5. DETERMINATION OF PERFORMANCE GOALS

The primary endpoints and associated performance goals (PGs) were developed after consulting FDA and are based on predicate submissions for the Shockwave Peripheral IVL System and supported by results of a recent meta-analysis on peripheral IVL and benchmark devices.

Specifically, prior FDA review of the original Peripheral IVL System 510(k) K161384 (cleared September 14, 2016) and predicate device Shockwave S4 510(k) K180454 (cleared June 27, 2018) was taken into consideration. K161384 included a pooled analysis of the Disrupt PAD I & II studies used to support substantial equivalence, and K180454 provided confirmatory clinical data from Disrupt BTK related to modifications to the cleared device.

As part of an ongoing clinical evaluation process, periodic literature searches are conducted to assess the ongoing benefit risk profile of the device. The most recent literature search and associated meta-analyses provide additional justification for the PGs for the pooled primary

analysis cohort. For details on the methodology used to conduct the meta-analyses on the relevant literature sources identified in the search, refer to Appendix B.

5.1. Performance Goal for Safety

As noted in Section 4.1, the primary safety endpoint for the pooled analysis cohort is MAE at 30 days. This is consistent with the pooled PAD I & II analysis and the Disrupt PAD BTK study, previously submitted to FDA in K161384 and K180454, respectively. MAE is a clinically relevant composite endpoint frequently used in peripheral vascular research [1-4]. Composites generated by the combination of individual endpoints provide additional statistical power to detect potentially meaningful differences between treatments [5].

In the pooled PAD I/II analysis, the PG for 30-day MAE was 8.7%. For the pooled primary safety hypothesis, a conservative 2.5% non-inferiority adjustment was applied to account for a more complex patient population in the JAVELIN studies including Rutherford Classification 5, dialysis patients, smaller diameter vessels, infrapopliteal lesions, and a higher rate of chronic total occlusions (CTOs). As a result, the primary safety endpoint PG for 30-day MAE is 11.2%.

The primary safety endpoint PG is further supported by the clinical literature for benchmark plaque-modifying devices designed to treat PAD. The literature review -described above identified 16 unique sources with at least 50 subjects and published within the last 10 years, representing 3,207 subjects, with complete data available for 30-day MAE (see Appendix B for details). Sample sizes ranged from 50 to 800, and the reported 30-day MAE rates ranged from 0.0% - 14.0% with associated 95% upper confidence limits ranging from 2.2 - 22.3%. The meta-analysis random effects model estimated a mean 30-day MAE rate of 2.8% (95% CI: 1.6-4.9).

As noted in Section 6.1 below, with a PG of 11.2% and 90 subjects, rejection of the null hypothesis would demonstrate an expected true population 30-Day MAE rate of 2.0% with an upper 2-sided 95% CI of less than or equal to 11.2% which are clinically and regulatory appropriate estimates based on prior investigations of peripheral IVL [1-3] and also consistent with the broader contemporary peripheral literature sources and meta-analysis (Appendix B).

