As noted in Section 6.2 below, with a PG of 85.0% and 90 subjects, rejection of the null hypothesis would demonstrate an expected true population rate of 97.0% with a lower 2-sided 95% CI of greater than or equal to 85% which are a clinically and regulatory appropriate estimates based on prior investigations of peripheral IVL [1-3] and -also consistent with the broader contemporary peripheral literature sources and meta-analysis. (Appendix B).

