6.1. Primary Safety Hypothesis

The primary safety hypothesis is:

$$H_0: \Pi_S > PG_S \text{ vs. } H_A: \Pi_S \leq PG_S$$

where Π_S is the proportion of patients who experience a MAE within 30 days of procedure and PG_S is the Safety Performance Goal.

All subjects in whom a Mini S IVL catheter was introduced into the vasculature will be included in the analysis (i.e., it is an intent-to-treat analysis). The hypothesis will be tested using a one-sided Exact Binomial Test at $\alpha=0.025$.

The assumptions for the sample size calculations are listed below.

- Expected 30-day MAE rate of 2.0% = Π_s
- Performance goal of 11.2% = PG_s
- One-sided statistical significance level of 0.025 = α
- The hypothesis will be tested using a one-sided Exact Binomial Test.
- Statistical power of 96.5%

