The literature review identified 9 unique sources, representing 2129 total subjects, that reported the percentage of cases with final residual stenosis <50% (see **Figure B2**). Sample sizes ranged from 52 to 733, and the reported rates ranged from 83.2% - 100%. In the meta-analysis, the common effects model estimated final residual stenosis <50% at 89.0% (95% CI: 87.5-90.4), and the random effects model estimated a rate of 92.5% (95% CI: 88.5-95.2). Residual heterogeneity was considered high with $I^2 = 80\%$.

Figure B2. Forest Plot for Final Residual Stenosis < 50%

Meta-Analysis Discussion

Substantial residual heterogeneity was observed in both analyses, represented by I^2 values greater than 70% and p-values associated with the I^2 of <0.01 . The I^2 value represents the percentage of all observed heterogeneity that is attributed to between-study variance in the true population proportion, and a significant p-value indicates that the null hypothesis of a single true population proportion (Π) has been rejected, and thus the point estimate represents a range of true population proportions. A high I^2 value indicates that, while the point estimate of the range of true population proportions is accurate, it will be less precise than is optimal for a performance goal that will be applied across a range of studies. The study hypotheses take these findings into consideration.

With a PG of 11.2% and 90 subjects, rejection of the null hypothesis would demonstrate an expected true population 30-Day MAE rate of 0.0-4.4% with an upper 2-sided 95% CI of less than or equal to 11.2% and with a PG of 85.0%. Rejection of the null effectiveness hypothesis would demonstrate an expected true population rate of 93.3 - 100.0% with a lower 2-sided 95% CI of greater than or equal to 85%. These results are clinically and regulatory appropriate estimates based on prior investigations of peripheral IVL [1-3] and are also consistent with the broader contemporary peripheral literature sources and meta-analysis.

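### SAP 5.1, 5.2 and Appendix B say rejection would demonstrate particular true rates; it shows only 30-day MAE below 11.2% and Technical Success above 85.0%

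*SAP*

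**What the plan says.** SAP 5.1, which justifies the safety performance goal, says that with 90 subjects "rejection of the null hypothesis would demonstrate an expected true population 30-Day MAE rate of 2.0"%. The rest of that sentence ties the claim to a confidence limit: the upper two-sided 95% bound would not exceed the goal of 11.2%. SAP 5.2 makes the parallel statement for effectiveness, that "rejection of the null hypothesis would demonstrate an expected true population rate of 97.0"%, with a lower limit of at least 85%.

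The discussion at the end of SAP Appendix B describes the same two rejections with different figures. For safety, "rejection of the null hypothesis would demonstrate an expected true population 30-Day MAE rate of 0.0-4.4"%. For effectiveness, "Rejection of the null effectiveness hypothesis would demonstrate an expected true population rate of 93.3 - 100.0"%. It repeats the same confidence limits.

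SAP 5.1 and 5.2 point to 6.1 and 6.2 for support. Those sections list 2.0% and 97.0% among the inputs to the sample-size calculation (for safety, "Expected 30-day MAE rate of 2.0"%, "Performance goal of 11.2"% and "One-sided statistical significance level of 0.025"). The hypotheses stated there concern only the performance goals. SAP 6.3 calls 2% and 97% assumed true rates.

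**The concern.** A test against a performance goal says which side of the goal the true rate lies on, subject to its error rate. It does not confirm the alternative at which the study was powered. The wording in 5.1 and 5.2 turns a design input into a finding. The wording in Appendix B takes the set of observed results that would pass and calls it a set of true rates.

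The pooled results are intended to support a 510(k) submission. If this wording were carried into a report, a narrow pass would be described as establishing a rate much better than the data support. Section 5 and Appendix B also use these statements to argue that the goals are appropriate, so that argument leans on a property the test does not have.

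**Working it through.** **Inputs.** N = 90, goals of 11.2% and 85.0%, assumed rates of 2.0% and 97.0%, and a one-sided exact binomial test at alpha 0.025 (SAP 6.1 to 6.3). Effectiveness is first treated as 90 independent units, which is what the stated power implies.

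**1. Reproduce the plan's figures.**

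Safety rejects if X ≤ c, where c is the largest count with P(X ≤ c | 90, 0.112) ≤ 0.025.
- c = 4 gives 0.0218 and c = 5 gives 0.0537, so the rule is at most 4 MAEs.
- Power is P(X ≤ 4 | 90, 0.02) = 0.9652. The SAP states 96.5%.

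Effectiveness rejects if X ≥ r, where r is the smallest count with P(X ≥ r | 90, 0.85) ≤ 0.025.
- r = 84 gives 0.0131 and r = 83 gives 0.0308, so the rule is at least 84 successes.
- Power is P(X ≥ 84 | 90, 0.97) = 0.9812. The SAP states 98.1%.

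Study-wide power is 0.965 × 0.981 = 0.947. The SAP states 94.7%. All three figures reproduce.

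**2. Identify the Appendix B ranges.** 0/90 = 0.0% and 4/90 = 4.4%; 84/90 = 93.3% and 90/90 = 100.0%. These are exactly the observed proportions that reject.

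**3. What a pass at the boundary supports.** Two-sided 95% Clopper-Pearson intervals:

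| Result | Interval | Decision |
|---|---|---|
| 4/90 MAE | 1.2% to 11.0% | rejects |
| 5/90 MAE | 1.8% to 12.5% | does not reject |
| 84/90 success | 86.1% to 97.5% | rejects |
| 83/90 success | 84.6% to 96.8% | does not reject |

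The intervals agree with the test, so the confidence-limit half of each SAP statement is right.

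**4. Could any result with 90 units establish the quoted rates?** With 0/90 MAEs the upper limit is 4.0%, still above 2.0%. With 90/90 successes the lower limit is 96.0%, still below 97.0%. An upper limit within 4.4% needs 0/90, because 1/90 gives 6.0%. A lower limit of at least 93.3% needs 89/90 (94.0%), because 88/90 gives 92.2%.

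**5. How often rejection occurs outside the quoted ranges.**
- True MAE rate 5%, 6%, 7%: P(X ≤ 4) = 0.53, 0.37, 0.24.
- True success rate 92.5%, 90%: P(X ≥ 84) = 0.48, 0.19.

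These are single-endpoint probabilities; study success needs both.

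**6. Dependence on the number of lesions.** Protocol 9.2.2 and SAP 6.2 count lesions, the protocol allows up to two per subject, and SAP Appendix A excludes unreadable images. If lesions were independent, the cutoff would be 93/100 (p = 0.0122; 92/100 gives 0.0275) or 110/120 (p = 0.0217; 109/120 gives 0.0420). The figure 93.3% therefore belongs to exactly 90 evaluable lesions.

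**7. Match between reported bounds and the test.** Protocol 9.2.1 and 9.2.2 report one-sided 95% bounds, which correspond to alpha 0.05. At 83/90 the one-sided 95% lower bound is 85.9%, above the goal, yet the test at 0.025 does not reject (p = 0.031). A two-sided 95% interval avoids that mismatch.

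**The case against.** The strongest defence is that the valid inference is already on the page. Each statement goes on to the confidence limit, the rates are qualified as expected, and 5.1 and 5.2 refer to sections that list 2.0% and 97.0% as assumptions. The objective in SAP 2, the hypotheses in 6.1 and 6.2 and the success rule in 6.3 are all framed against the goals. This stands, and it limits the point to interpretation. It does not rescue the wording, because the thing said to be demonstrated is still a true population rate.

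A reader might infer more, and the documents do not support it:

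- **That this is the SAP's rule for reporting a positive trial.** It sits in the rationale for the goals and in a literature appendix. No reporting section tells anyone to state 2.0% or 97.0%; SAP 9.1 and Appendix A provide for summaries of observed data.
- **That 97.0% conflicts with the meta-analysis because it exceeds 88.5-95.2%.** That interval is for a random-effects mean. With I² of 80% and study rates from 83.2% to 100%, it does not rule out 97% for one device.
- **That the sections flatly contradict each other.** 2.0% lies within 0.0-4.4% and 97.0% within 93.3-100.0%. They are different descriptions of the same event, both mislabelled.
- **That the pass probabilities in step 5 are wrong decisions.** A true MAE rate of 5-7% is below 11.2%, and 92.5% success is above 85%, so rejecting is correct. The figures show only that rejection does not pin down the quoted rates.

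**Conclusion.** The point holds as an error of interpretation in three places. Rejection shows a true 30-day MAE rate below 11.2% and a true Technical Success rate above 85.0%, each at one-sided 2.5%, and nothing tighter. The gap is material at the boundary: an interval reaching 11.0% against a claimed 2.0% or 0.0-4.4%, and one starting at 86.1% against a claimed 97.0% or 93.3-100.0%.

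The decision rule, sample size, alpha and power stand. The counts assume 90 evaluable subjects for safety and 90 independent evaluable lesions for effectiveness. Other lesion numbers move the effectiveness cutoff but not the conclusion.

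**What to change.** - In SAP 5.1, 5.2 and Appendix B, keep the confidence-limit statement and delete the claim that a true rate of 2.0%, 97.0%, 0.0-4.4% or 93.3-100.0% is demonstrated. Say instead that rejection shows, at one-sided 2.5%, a true MAE rate below 11.2% and true Technical Success above 85.0%.
- Label 2.0% and 97.0% as planning assumptions wherever they appear.
- Label 0.0-4.4% and 93.3-100.0% as observed rates that meet the goals, illustrative for exactly 90 evaluable units. Do not fix 84 of 90 as the effectiveness cutoff; state that it is recalculated for the actual number of evaluable lesions.
- Report observed rates with two-sided 95% Clopper-Pearson intervals, which match one-sided alpha 0.025, and reconcile the one-sided 95% bounds in Protocol 9.2.1 and 9.2.2 with this.

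The cost is wording only, with no change to design, data or sample size. The stated conclusion becomes less favourable.

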5.2. Performance Goal for Effectiveness

As noted in Section 4.2, the primary effectiveness endpoint for the pooled analysis cohort is Technical Success defined as final residual stenosis $\leq 50\%$ without flow-limiting dissection (\geq Grade D) of the target lesion by angiographic core lab. The stenosis threshold used in this definition ($\leq 50\%$) is consistent with the effectiveness endpoints used in the Disrupt PAD I & II (K161384) pooled analysis and the Disrupt PAD BTK study (K180454). Technical Success is a clinically relevant outcome given the highly stenotic lesions targeted in the Mini S studies and is supported by published standards for clinical trial endpoints [9]. Consensus definitions from the Peripheral Academic Research Consortium (PARC) note that acute technical success for peripheral revascularization is defined as the achievement of a final residual diameter stenosis $< 30\%$ for stent and $< 50\%$ for angioplasty or atherectomy by angiography at the end of the procedure (and without flow-limiting arterial dissection or hemodynamically significant

translesional pressure gradient < 10 mm Hg) for endovascular revascularization [9]. Clinical evidence from the Disrupt PAD studies demonstrates a dramatic reduction in the need for bailout stents and justifies the 50% threshold [10].

In the pooled PAD I/II analysis, the PG for the effectiveness endpoint was 89.3%. For the pooled JAVELIN primary effectiveness hypothesis, a 5% non-inferiority adjustment was applied to account for a more complex patient population in JAVELIN studies including small vessel diameters, infrapopliteal vessels and a higher rate of CTOs. As a result, the primary effectiveness PG for the JAVELIN program is 85.0% for Technical Success.

The primary effectiveness endpoint PG is further supported by the clinical literature for benchmark plaque-modifying devices designed to treat PAD. The literature review -described in Section 5 identified 9 unique sources, with at least 50 subjects and published since 2013, representing 2129 total subjects, that reported the percentage of cases with final residual stenosis <50% (see Appendix B). Sample sizes ranged from 52 to 733, and the reported rates ranged from 83.2% - 100% with associated 95% lower confidence limits ranging from 76.2 – 94.9%. The meta-analysis random effects model based on these studies estimated a mean rate of 92.5% (95% CI: 88.5-95.2).

As noted in Section 6.2 below, with a PG of 85.0% and 90 subjects, rejection of the null hypothesis would demonstrate an expected true population rate of 97.0% with a lower 2-sided 95% CI of greater than or equal to 85% which are a clinically and regulatory appropriate estimates based on prior investigations of peripheral IVL [1-3] and -also consistent with the broader contemporary peripheral literature sources and meta-analysis. (Appendix B).

6. HYPOTHESES AND SAMPLE SIZE CONSIDERATIONS

The following hypotheses and associated PGs for the primary safety and effectiveness endpoints are both clinically and statistically relevant to demonstrate study success and supported by the results of the meta-analysis (Appendix B).

6.1. Primary Safety Hypothesis

The primary safety hypothesis is:

$$H_0: \Pi_S > PG_S \text{ vs. } H_A: \Pi_S \leq PG_S$$

where Π_S is the proportion of patients who experience a MAE within 30 days of procedure and PG_S is the Safety Performance Goal.

All subjects in whom a Mini S IVL catheter was introduced into the vasculature will be included in the analysis (i.e., it is an intent-to-treat analysis). The hypothesis will be tested using a one-sided Exact Binomial Test at $\alpha=0.025$.

The assumptions for the sample size calculations are listed below.

- Expected 30-day MAE rate of 2.0% = Π_s
- Performance goal of 11.2% = PG_s
- One-sided statistical significance level of 0.025 = α
- The hypothesis will be tested using a one-sided Exact Binomial Test.
- Statistical power of 96.5%

6.2. Primary Effectiveness Hypothesis

The primary effectiveness hypothesis is:

$$H_0: \Pi_E \leq PG_E \quad \text{vs.} \quad H_A: \Pi_E > PG_E$$

where Π_E is the proportion of target lesions with technical success and PG is the effectiveness Performance Goal.

The assumptions for the sample size calculations are listed below.

- Expected Technical Success rate of 97.0% = Π_E
- Performance goal of 85.0% = PG_E
- One-sided statistical significance level of 0.025 = α
- The hypothesis will be tested using a one-sided Exact Binomial Test.
- Statistical power of 98.1%.

6.3. Sample Size Justification

The study will be deemed a success if both the primary safety and effectiveness endpoints are met. To provide at least 80% power study-wide, each endpoint was powered to at least 90%. A one-tailed scenario was used to assess the minimum sample size needed to detect a difference in the assumed true rate of safety (2%) versus the safety performance goal of 11.2%. The same calculation was done for the assumed true rate of effectiveness (97%) versus the performance effectiveness goal of 85%. A sample size of 90 subjects provides a study-wide power of 94.7% to meet both the safety and effectiveness endpoints. No adjustments for multiplicity are needed.

7. POOLABILITY

Results for the first 90 consecutively enrolled evaluable subjects across both studies (with a minimum of 50% of patients from the US) will comprise the primary analysis cohort and will be submitted to support a Premarket Notification 510(k) submission.

Justification of poolability is based on the following: The Mini S Australia and New Zealand and the FORWARD IDE Study protocols share the same eligibility criteria, data collection requirements, and IVL treatment algorithm and patient follow-up procedures. Both studies utilize the same electronic data capture system, are monitored with 100% source document

verification, include independent angiographic and duplex core labs, independent clinical events committee (CEC) for endpoint adjudication of MAE, and data safety monitor (DSM). Both studies use the standard and flex configurations of the JAVELIN IVL Catheter.

Primary endpoints will be analyzed using a logistic regression model including an intercept term and fixed effect for geographical region to determine whether any significant differences exist. The tests will be performed at a 15% level of significance level. A significant result will require further inspection of the by-region results to assess the reasons for differences and to evaluate whether pooling across geographies is appropriate.

8. ANALYSIS SET

The primary analysis cohort will be the first 90 consecutively enrolled evaluable subjects across both studies (with a minimum of 50% of patients from the US), which will be submitted to support a Premarket Notification 510(k) application.

9. STATISTICAL METHODS OF ANALYSES

9.1. General Considerations

Descriptive statistics will be provided in this clinical study. Analyses will be reported on at pre-specified time points including 30 days, 6, and 12 months.

Categorical variables will be summarized by the number of non-missing observations, and the frequency and percentage for each category. Unless otherwise noted, missing data will be excluded from the denominator.

Continuous variables will be summarized by the mean, standard deviation, median, IQR, minimum, and maximum.

Statistical analyses will be performed using SAS System® Version 9.4 or higher.

9.2. Baseline Characteristics

The following will be carried out for all subjects: demographic, medical history and other clinically relevant baseline variables will be summarized using the appropriate descriptive statistics as described above.

9.3. Handling of Dropouts and Missing Data

No imputation of or adjustments for missing data will be performed for the primary analyses. All available data will be presented. For time to event analyses, subjects who do not experience the event in question will be censored at their last known follow-up.

For the primary safety endpoint analysis, the denominator for each parameter in the safety measures will be the number of subjects who had sufficient follow up (at least 23 days for 30-day visit) plus any subjects who had an event prior to the milestone visit.

10. ADDITIONAL DATA SUMMARIES / SUPPLEMENTAL ANALYSES

10.1. Subgroup Analyses

Analyses to examine the consistency of results across different subgroups will be performed for the primary safety and effectiveness endpoints for the following subgroups, and results will be reported using descriptive statistics:

- Geography (US, OUS)
- Above the knee (ATK) lesions vs below the knee (BTK) lesions

To support the subgroup analyses, a minimum of 15 subjects with BTK lesions, and a minimum of 15 subjects in each geography will be included. No formal hypothesis testing for subgroup analyses is pre-specified. However, to examine the consistency of results across different subgroups, the primary safety and effectiveness endpoints will be compared between subgroups using a logistic regression model including an intercept term and fixed effect for the subgroup, with corresponding 95% confidence interval and p-value presented. Additional analyses of group differences will be completed if the subgroup term in the model has a p-value of ≤ 0.15 .

